4.2.4.2 Laboratory assessments

Data obtained up until the 90 days following discontinuation of study treatment or until the initiation of the first subsequent anti-cancer therapy (including radiotherapy, with the exception of palliative radiotherapy) following discontinuation of study treatment (whichever occurs first) will be used for reporting. This will more accurately depict laboratory toxicities attributable to study treatment only as a number of toxicities up to 90 days following discontinuation of the study treatment are likely to be attributable to subsequent therapy.

However, to assess the longer term toxicity profile, some summaries of laboratory data may be produced containing data collected up until 90 days following discontinuation of the study treatment (i.e., without taking subsequent therapy into account).

Any data post 90 days after the last dose of the study treatment will not be summarised.

Data summaries will be provided in preferred units.

Scatter plots (shift plots) of baseline to maximum value/minimum value (as appropriate) on treatment (i.e. on-treatment is defined as data collected between the start of treatment and the relevant follow-up period following the last dose of study treatment) may be produced for certain parameters if warranted after data review.

Box-plots of absolute values by week, and box-plots of change from baseline by week, may be presented for certain parameters if warranted after data review. For continuous laboratory assessments absolute value and change from baseline will be summarised using descriptive statistics at each scheduled assessment time by actual treatment group.

Shift tables for laboratory values by worst CTCAE grade will be produced, and for specific parameters separate shift tables indicating hyper- and hypo- directionality of change will be produced. The laboratory parameters for which CTCAE grade shift outputs will be produced are:

- Haematology: Haemoglobin; Leukocytes; Lymphocytes (count, absolute); Neutrophils (count, absolute); Platelets
- Clinical chemistry: ALT, AST, ALP, Total Bilirubin, Albumin, Magnesium – hypo and – hyper, Sodium – hypo and – hyper, Potassium – hypo and – hyper, Corrected Calcium – hypo and – hyper, Glucose – hypo and – hyper, Creatinine.

Additional summaries will include a shift table for urinalysis (Bilirubin, Blood, Glucose, Ketones, Protein) comparing baseline value to maximum on-treatment value.

Liver Enzyme Elevations and Hy's law

The following summaries will include the number (%) of patients who have:

- Elevated ALT, AST, and Total bilirubin during the study
 - ALT $\geq 3x$ – $\leq 5x$, $> 5x$ – $\leq 8x$, $> 8x$ – $\leq 10x$, $> 10x$ – $\leq 20x$, and $> 20x$ Upper Limit of Normal (ULN) during the study
 - AST $\geq 3x$ – $\leq 5x$, $> 5x$ – $\leq 8x$, $> 8x$ – $\leq 10x$, $> 10x$ – $\leq 20x$, and $> 20x$ ULN during the study
 - Total bilirubin $\geq 2x$ – $\leq 3x$, $> 3x$ – $\leq 5x$, $> 5x$ ULN during the study
 - ALT or AST $\geq 3x$ – $\leq 5x$, $> 5x$ – $\leq 8x$, $> 8x$ – $\leq 10x$, $> 10x$ – $\leq 20x$, $> 20x$ ULN during the study
 - ALT or AST $\geq 3x$ ULN and Total bilirubin $\geq 2x$ ULN during the study (Potential Hy's law): The onset date of ALT or AST elevation should be prior to or on the date of Total Bilirubin elevation

Liver biochemistry test results over time for patients with elevated ALT or AST (ie $\geq 3x$ ULN), and elevated Total Bilirubin (ie $\geq 2x$ ULN) (at any time) will be plotted. Individual patient data where ALT or AST (ie $\geq 3x$ ULN) plus Total Bilirubin (ie $\geq 2x$ ULN) are elevated at any time will be listed also.

Plots of ALT and AST vs. Total Bilirubin by treatment group will also be produced with reference lines at $3\times\text{ULN}$ for ALT, AST, and $2\times\text{ULN}$ for Total Bilirubin. In each plot, Total Bilirubin will be in the vertical axis.

4.2.4.3 ECGs

ECG data obtained up until the safety follow-up will be included in the summary tables.

Overall evaluation of ECG is collected at each visit in terms of normal or abnormal, and the relevance of the abnormality is termed as “clinically significant” or “not clinically significant”. A shift table of baseline evaluation to worst evaluation on-treatment will be produced.

4.2.4.4 Vital signs

Vital signs data obtained up until the 30 day safety follow-up visit will be included in the summary tables.

Box plots for absolute values and change from baseline by week may be presented for certain vital signs parameters if warranted after data review.

Vital signs (systolic blood pressure (SBP), diastolic blood pressure (DBP), pulse rate, temperature, respiratory rate and weight) will be summarised over time in terms of absolute values and change from baseline at each scheduled measurement by actual treatment group

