#### 5.5.3.1 **MEDI4736 adverse events of special interest**

An adverse event of special interest (AESI) is one of scientific and medical interest specific to understanding of the Investigational Product and may require close monitoring and rapid communication by the Investigator to the sponsor. An AESI may be serious or non-serious. The rapid reporting of AESIs allows ongoing surveillance of these events in order to characterize and understand them in association with the use of this investigational product. Unless they meet SAE criteria, AESIs will not be recorded during the Extension Study.

The AESIs for MEDI4736 include but are not limited to events with a potential inflammatory or immune-mediated mechanism and which may require more frequent monitoring and/or interventions such as steroids, immunosuppressants and/or hormone replacement therapy. These AESIs are being closely monitored in clinical studies with MEDI4736 monotherapy and combination therapy. An AESI is defined as an adverse event that is associated with drug

exposure and is consistent with an immune-mediated mechanism of action and where there is no clear alternate aetiology. Serologic, immunologic, and histologic (biopsy) data, as appropriate, should be used to support an irAE diagnosis. Appropriate efforts should be made to rule out neoplastic, infectious, metabolic, toxin, or other etiologic causes of the irAE.

If the Investigator has any questions in regards to an AE being an irAE, the Investigator should promptly contact the Study Physician.

AESIs observed with MEDI4736 include:

- Diarrhoea / colitis and intestinal perforation
- Pneumonitis / interstitial lung disease
- hepatitis / transaminase increases
- Endocrinopathy (ie, events of hypophysitis / hypopituitarism, adrenal insufficiency, hyper- and hypothyroidism and type I diabetes mellitus)
- Rash / dermatitis
- Nephritis / blood creatinine increases
- Pancreatitis / serum lipase and amylase increases
- Myocarditis
- Myositis / polymyositis
- Neuropathy / neuromuscular toxicity (eg, Guillain-Barré, and myasthenia gravis)
- Other inflammatory responses that are rare / less frequent with a potential immune-mediated aetiology include, but are not limited to, pericarditis, sarcoidosis, uveitis and other events involving the eye, skin, haematological and rheumatological events.

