### **Adverse events based on examinations and tests**

The results from protocol mandated laboratory tests and vital signs will be summarised in the CSR. Deterioration as compared to baseline in protocol-mandated laboratory values and vital signs should therefore only be reported as AEs if they fulfil any of the SAE criteria or are the reason for discontinuation of treatment with the investigational product. An abnormal laboratory finding (including ECG findings) that requires an action or intervention by the Investigator, or a finding judged by the Investigator to represent a change beyond the range of normal physiologic fluctuation, should also be reported as an AE.

If deterioration in a laboratory value/vital sign is associated with clinical signs and symptoms, the sign or symptom will be reported as an AE and the associated laboratory result/vital sign will be considered as additional information. Wherever possible the reporting Investigator uses the clinical, rather than the laboratory term (eg, anaemia versus low haemoglobin value). In the absence of clinical signs or symptoms, clinically relevant deteriorations in non-mandated parameters should be reported as AE(s).

Asymptomatic Grade 3 or 4 increases in amylase or lipase resulting in interruption of dosing (refer to Section 5.5.3) should be reported as AEs.

Deterioration of a laboratory value, which is unequivocally due to disease progression, should not be reported as an AE/SAE.

Any new or aggravated clinically relevant abnormal medical finding at a physical examination as compared with the baseline assessment will be reported as an AE.

**NB.** Cases where a patient shows an AST **or** ALT  $\geq 3$  x ULN **or** total bilirubin  $\geq 2$  x ULN may need to be reported as SAEs. These cases should be reported as SAEs if after evaluation they meet the criteria for a Hy's Law case or if any of the individual liver test parameters fulfil any of the SAE criteria. For potential Hy's Law to be met, the elevation in transaminases must precede or be coincident with (ie, on the same day) the elevation in total bilirubin, but there is no specified timeframe within which the elevations in transaminases and total bilirubin must occur. Please refer to [Appendix E](#) 'Actions required in cases of combined increase of Aminotransferase and Total Bilirubin – Hy's Law', for further instructions in cases of combined increases of aminotransferase and total bilirubin.

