#### **6.4.8 Vital signs**

For timings of assessments refer to the study plans in Table 1 (Screening and the Treatment Period), Table 2 (for follow-up of patients achieving disease control or who are discontinued due to toxicity or a reason other than confirmed PD) and Table 3 (for follow-up of patients discontinuing due to confirmed PD). Patients receiving re-treatment after final DCO for the study are to undergo vital signs assessments as clinically indicated at the discretion of the Investigator and per local standard of care; data will be recorded on patient charts but will not otherwise be reported for the purposes of this study.

Patients will be monitored with assessment of vital signs (BP, pulse, respiratory rate, temperature and oxygen saturation) at Screening and on the day of each infusion and in the follow-up period on Day 30. On infusion days vital signs will all be taken before the infusion. Blood pressure and pulse will also be collected during and after the infusion (see Section 6.4.8.1).

Additional monitoring with assessment of vital signs is at the discretion of the Investigator per standard clinical practice or as clinically indicated.

Additional recording of vital signs may be captured on an unscheduled vital signs eCRF and on the eCRF for AE/SAE where applicable. The date and time of collection and measurement will be recorded on the appropriate eCRF.

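### SAP 4.2.4.4 omits oxygen saturation from the vital-sign summaries that the protocol gives as its reason for limiting adverse event reporting

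*SAP*

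**What the plan says.** On vital signs, three places belong together.

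- Protocol 6.4.3 (Adverse events based on examinations and tests) states: "The results from protocol mandated laboratory tests and vital signs will be summarised in the CSR". It then draws a consequence: deterioration from baseline in those measurements "should therefore only be reported as AEs if they fulfil any of the SAE criteria or are the reason for discontinuation of treatment". The same section adds other routes to an adverse event report, set out in the check below.
- Protocol 6.4.8 defines the set: "Patients will be monitored with assessment of vital signs (BP, pulse, respiratory rate, temperature and oxygen saturation) at Screening and on the day of each" dosing visit; a further set is due at Day 30 of follow-up. Section 6.4.8.2 places the saturation reading before the infusion.
- SAP 4.2.4.4 names what will be tabulated: "Vital signs (systolic blood pressure (SBP), diastolic blood pressure (DBP), pulse rate, temperature, respiratory rate and weight) will be summarised over time", as absolute values and change from baseline by treatment group. Box plots are optional there.

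On laboratory tests, SAP 4.2.4.2 introduces a fixed list with the words "The laboratory parameters for which CTCAE grade shift outputs will be produced are". Lipase, amylase and thyroid tests are not on it. Protocol 5.5.3.1 names "Pancreatitis / serum lipase and amylase increases" as an event of special interest, and lists hyper- and hypothyroidism under endocrinopathy.

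**The concern.** The protocol makes a trade. Sites report fewer deteriorations as adverse events because the measurements themselves will be shown in the report. That works only if every mandated measurement covered by the rule has a table. Oxygen saturation is covered by the rule and has none.

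The omission matters more here than it would in most trials. Patients enter within 42 days of their last radiation session. Protocol 5.5.3.1 says radiation pneumonitis usually shows itself 1 to 3 months after radiotherapy and is hard to diagnose, and it names pneumonitis and interstitial lung disease as events of special interest. Of the routine vital signs, oxygen saturation bears most directly on that risk. What is at stake is a randomised comparison of saturation that the trial has the data to make but does not plan.

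**Working it through.** No arithmetic beyond counting applies. The check compares lists and follows the reporting rules.

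**1. Vital-sign lists.**

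| Protocol 6.4.8 | SAP 4.2.4.4 |
|---|---|
| Blood pressure | Systolic and diastolic |
| Pulse | Listed |
| Respiratory rate | Listed |
| Temperature | Listed |
| Oxygen saturation | Absent |
| (not in this list) | Weight |

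Four of the five protocol vital signs are carried over, weight is added, and only oxygen saturation is dropped.

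**2. Is it covered elsewhere in the SAP?** Section 3.4.4 derives change from baseline for vital signs without naming them, but that is a derivation, not an output. Section 4.2.4 allows further safety summaries without committing to any. The special-interest tables in 4.2.4.1 are built from reported events, so they cannot recover a reading that was never reported. Section 6, which records changes from the protocol, does not mention the omission. It looks like an oversight.

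**3. Which falls in saturation become adverse events under Protocol 6.4.3?**

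- Meets a seriousness criterion: yes.
- Is the reason for stopping treatment: yes.
- Comes with clinical signs and symptoms: the sign or symptom is reported.
- Comes with a new, clinically relevant physical examination finding: that finding is reported.
- Needs action, or is "a finding judged by the Investigator to represent a change beyond the range of normal physiologic fluctuation, should also be reported as an AE": this clause is written for laboratory and ECG findings, not vital signs.
- Is clinically relevant but without symptoms: this clause covers only measurements the protocol does not mandate, and saturation is mandated.

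What remains is an isolated fall, neither serious nor treatment-limiting, with no accompanying sign or symptom. Steps 1 and 2 show that it has no planned table.

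**4. Laboratory tests.** Protocol Table 6 has 20 chemistry analytes. The SAP shift list has 11 chemistry parameters, so 20 - 11 = 9 are left out, lipase and amylase among them. However, SAP 4.2.4.2 also summarises continuous laboratory assessments by visit and arm, which covers both enzymes. SAP 3.4.2 derives CTCAE grades, low/normal/high classes and on-treatment extremes. Under Protocol 6.4.3, findings that need action or exceed normal fluctuation are adverse events, as are asymptomatic Grade 3 or 4 amylase or lipase rises that interrupt dosing. What is missing for the enzymes is a graded display of individual outliers, which by-visit means can hide.

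Thyroid tests are less clear. SAP 3.4.2 refers to Protocol 6.4.5, which names them, but the SAP itself never does, and it calculates change from baseline only for haematology and chemistry.

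**The case against.** The best counter-argument is that the gap is small and that existing outputs cover the clinical risk. Pneumonitis is an event of special interest and is tabulated by grade, onset and outcome once reported. The respiratory system is part of the physical examination, adverse events revealed by observation are collected, and the SAP leaves room for extra safety tables. Choosing which analytes get shift tables is ordinary output design. Most of this stands. It limits the point to isolated falls in saturation and makes the laboratory additions optional. It does not supply the missing summary, because an option to add tables is not a commitment.

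Four stronger readings are tempting, and the documents do not support them.

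- A reader might infer that sites are told not to report deteriorating vital signs. Protocol 6.4.3 restricts reporting, with exceptions; it does not forbid it.
- A reader might infer that signals of pneumonitis, pancreatitis and thyroid disease can all go unreported. Step 4 shows the laboratory routes, and reported pneumonitis is tabulated.
- A reader might infer that the promised laboratory summary does not exist. For lipase and amylase it does, by visit; for thyroid tests the wording is unclear, which is not proof of absence.
- A reader might infer that the safety objective is not met. It names vital signs and laboratory findings in general and does not single out saturation.

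**Conclusion.** The point holds for oxygen saturation. The reporting rule rests on a summary that the SAP does not plan for this one vital sign. It is a cheap improvement to the safety outputs; it affects neither type I error nor any efficacy analysis.

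Its size cannot be put as a number. Counting scheduled readings would measure data volume, not missed signals. The protocol's 5% to 15% pneumonitis figure describes patients irradiated for breast, lung and mediastinal tumours; it is not a rate of silent desaturation. The documents give no such rate.

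The conclusion assumes that the list in SAP 4.2.4.4 is meant to be complete, and that no table specification outside these documents adds saturation. The laboratory part is secondary: a missing graded display for two enzymes whose increases are themselves a named event of special interest, and unclear coverage of thyroid tests.

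**What to change.** In SAP 4.2.4.4, add oxygen saturation to the by-visit summaries. Also tabulate, by arm, each patient's minimum on-treatment value and its change from baseline. Presented as continuous values, these need no cut-offs, and SAP 4.1.3 already says how on-treatment extremes are taken.

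Optionally, in SAP 4.2.4.2, add lipase and amylase to the CTCAE shift list, and add a low/normal/high shift table for TSH and T4 using the classification in SAP 3.4.2.

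No new data are needed. The cost is SAP wording, a few descriptive tables and a slightly longer safety output. The protocol synopsis says that the planned analyses had concluded by Amendment 07, so the tables could now be produced as additional safety summaries, which SAP 4.2.4 permits.

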4.2.4.5 Physical examination

Individual physical examination data will not be summarised.

4.2.4.6 Other safety data

Data from positive pregnancy tests will not be summarised.

4.2.5 WHO performance status

All WHO performance status data will be summarised over time for the ITT population.

4.2.6 PK analysis

MEDI4736 concentration data will be listed, and a summary will be provided for all evaluable patients. These outputs will be produced by AstraZeneca/MedImmune Clinical Pharmacology group or designee.

4.2.7 Immunogenicity analysis

Immunogenicity results will be listed and a summary will be provided of the number and percentage of patients who develop detectable anti-MEDI4736 antibodies based on the safety population. The immunogenicity titre and neutralising ADA data will be listed for samples confirmed positive for the presence of anti-MEDI4736 antibodies. The effect of immunogenicity on PK, PDx, efficacy and safety will be evaluated if data allow. These outputs will be produced by AstraZeneca/MedImmune Clinical Pharmacology group or designee.

4.2.8 PK/PDx relationships

If the data are suitable, the relationship between MEDI4736 PK exposure and efficacy/safety parameters may be investigated graphically or using appropriate data modelling approach. These outputs will be produced by AstraZeneca/MedImmune Clinical Pharmacology group or designee.

4.2.9 Exploratory endpoints

4.2.9.1 EQ-5D-5L

The change from baseline in health state utility values and the visual analogue scale will be compared between treatment arms at each visit using a mixed model repeated measures analysis, which adjusts for the same factors as the primary analysis and also the baseline health state utility value/visual analogue scale as appropriate. Adjusted mean differences between treatments and 95% CIs from these analyses will be presented, but, as this analysis is exploratory in nature, p-values will not be calculated. Further detail of this analysis will be provided in the payer analysis plan.

Descriptive statistics will be reported for health state domain (e.g., proportion in each domain) and the visual analogue scale by visit, as well as the change in the visual analogue scale value and the derived utility index value from baseline.

To support future economic evaluations, additional appropriate analyses may be undertaken, for example, mean health state utility pre- and post-treatment, and pre- and post-progression. These exploratory analyses may be carried out to support health authority appraisals and will consequently not be reported in the CSR. Further detail will be provided in the payer analysis plan.

A summary of compliance rate and evaluability rate will be provided for each treatment arm, by assessment time point and also for overall as appropriate.

4.2.9.2 Health resource use

An exploratory health economic analysis of hospital episodes including the number of hospitalisations, type of contact (hospitalisation, outpatient, day case), reason, total length of hospital stay and total length of ICU stay will be undertaken to examine the impact of disease and treatment on resource use to primarily support the economic evaluation of MEDI4736. This will include providing descriptive statistics as appropriate, including means, median,

ranges or frequencies and percentages and will be summarised by randomised treatment arm. These simple summaries will be included in the CSR. However, the exploratory health economic analysis to be performed will be described in the payer analysis plan.

4.2.10 Demographic and baseline characteristics data

The following will be summarised for all patients in the FAS (unless otherwise specified) by treatment group:

- Patient disposition (including screening failures and reason for screening failure)
- Important protocol deviations
- Inclusion in analysis populations
- Demographics (age, age group [<50 , ≥ 50 - < 65 , ≥ 65 years and additionally ≥ 75 years], sex, race and ethnicity)
- Patient characteristics at baseline (height, weight, weight group, body mass index (BMI) and BMI group)
- Patient recruitment by country and centre
- Previous disease-related treatment modalities
- Time from initial diagnosis to randomization
- Disease characteristics at baseline (WHO performance status, primary tumour location, histology type, tumour grade and overall disease classification, best response to previous therapy)
- Extent of disease at baseline
- TNM classification at baseline
- Medical history (past and current)
- Relevant surgical history (as appropriate)
- Physical examination at baseline
- Disallowed concomitant medications
- Allowed concomitant medications
- Post-discontinuation cancer therapy

- Nicotine use, categorised (never, current, former)
- Stratification factors as per IVRS and eCRF data

The AZ drug dictionary (AZDD) will be used for concomitant medication coding.

Patient disposition data will also be summarised at the time of OS analysis.

